9.2.3 Other Endpoints

The survey includes HCP characteristics and other outcomes that may be treated as covariates for data analysis. These questions are described in Table 9-2.

Table 9-2 Other outcomes collected in the survey

Data collected	Variable type	Operation definition/derivation
Years practicing as a physician	Categorical	< 5 years, 5 to <10 years, 10 to <15 years, ≥15 years, prefer not to answer
Number of patients for which the HCP has prescribed ENJAYMO™	Categorical	None, <5 patients, 5-10 patients, >10 patients, prefer not to answer
HCP confirmed distribution of the ENJAYMO™ Patient Guide	Categorical	Yes, no, I don’t know/am not sure
HCP confirmed vaccination status in the patient most recently prescribed ENJAYMO™	Categorical	Yes, no, I don’t know/am not sure
Vaccines HCP checked in the patient most recently prescribed ENJAYMO™	Categorical	Meningococcal conjugate vaccine(s), meningococcal serogroup B vaccine(s), pneumococcal vaccine(s), Other (please specify), I don’t know/am not sure
Vaccines up-to-date in the patient most recently prescribed ENJAYMO™	Categorical	Yes, no, I don’t know/am not sure
HCP administered or prescribed vaccines to the patient most recently prescribed ENJAYMO™	Categorical	Yes, no, I don’t know/am not sure
Reason HCP did not provide vaccines to the patient most recently prescribed ENJAYMO™	Categorical	The patient refused vaccination, the patient received vaccination elsewhere, I don’t know/am not sure
Timing of vaccination relative to starting ENJAYMO™ in the patient most recently prescribed ENJAYMO™	Categorical	At the same time ENJAYMO™ treatment was started, less than two weeks before ENJAYMO™ treatment was started, two weeks before ENJAYMO™ treatment was started, I don’t know/am not sure

HCP counselled the patient most recently prescribed ENJAYMO™ to seek immediate medical attention if they experience symptoms of serious infection	Categorical	Yes, no, I don't know/am not sure
Investigator in ENJAYMO™ clinical trial	Categorical	Yes, no, prefer not to answer
Involvement with CADENCE patient registry	Categorical	Yes, no, prefer not to answer

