[ON-LINE SURVEY - PROGRAMMER: RANDOMISE THE ORDER OF THE FIRST 5 RESPONSE OPTIONS]

HCP CHARACTERISTICS

[Preamble 2]: Below are 7 additional questions to help us combine your answers with other answers we have received, and to help us interpret the survey results. **THERE ARE NO CORRECT RESPONSES TO QUESTIONS 10, 11, 19, and 20. DISPLAY QUESTIONS 12-18 ON THE SAME PAGE.**

10. Approximately how many years have you been practicing as a physician?
- <5 years
 - 5 to <10 years
 - 10 to <15 years
 - ≥15 years
 - Prefer not to answer
11. Approximately how many patients have you treated with ENJAYMO™ (sutimlimab)?
- None → **PROCEED TO QUESTION 20**
 - < 5 patients → **PROCEED TO QUESTION 12**
 - 5-10 patients → **PROCEED TO QUESTION 12**
 - >10 patients → **PROCEED TO QUESTION 12**
 - Prefer not to answer → **PROCEED TO QUESTION 20**
12. For the most recent patient you prescribed ENJAYMO™ (sutimlimab), did you provide the patient with a copy of the ENJAYMO™ Patient Guide?
- Yes → **PROCEED TO QUESTION 13**
 - No → **PROCEED TO QUESTION 13**
 - I don't know/am not sure → **PROCEED TO QUESTION 13**
13. For the most recent patient you prescribed ENJAYMO™ (sutimlimab), did you confirm that their vaccination status is up-to-date according to local guidelines or recommendations for patients with persistent complement deficiencies?
- Yes → **PROCEED TO QUESTION 14**
 - No → **PROCEED TO QUESTION 19**
 - I don't know/am not sure → **PROCEED TO QUESTION 19**

14. For the most recent patient you prescribed ENJAYMO™ (sutimlimab), which vaccines did you check the status of? Please select all that apply.
- Meningococcal conjugate vaccine(s)
 - Meningococcal serogroup B vaccine(s)
 - Pneumococcal vaccine(s)
 - Other (not listed above); specify: _____
 - I don't know/am not sure
15. For the most recent patient you prescribed ENJAYMO™ (sutimlimab), was the patient up-to-date on their vaccinations?
- Yes → **PROCEED TO QUESTION 19**
 - No → **PROCEED TO QUESTION 16**
 - I don't know/am not sure → **PROCEED TO QUESTION 19**
16. For the most recent patient you prescribed ENJAYMO™ (sutimlimab), did you administer or prescribe vaccines to the patient?
- Yes → **PROCEED TO QUESTION 18**
 - No → **PROCEED TO QUESTION 17**
 - I don't know/am not sure → **PROCEED TO QUESTION 19**
17. For the most recent patient you prescribed ENJAYMO™ (sutimlimab), what was the reason you did not provide vaccination?
- The patient refused vaccination → **PROCEED TO QUESTION 19**

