 - The patient received vaccination elsewhere → **PROCEED TO QUESTION 18**
 - I don't know/am not sure → **PROCEED TO QUESTION 19**
18. For the most recent patient you prescribed ENJAYMO™ (sutimlimab), when were vaccinations administered relative to starting of ENJAYMO™ (sutimlimab)?
- At the same time ENJAYMO™ treatment was started
 - Less than two weeks before ENJAYMO™ treatment was started
 - Two weeks before ENJAYMO™ treatment was started
 - I don't know/am not sure

19. For the most recent patient you prescribed ENJAYMO™ (sutimlimab), did you counsel them to seek immediate medical attention if they experience symptoms associated with risks of serious infections or meningococcal infections associated with ENJAYMO™ (sutimlimab)?
- Yes
 - No
 - I don't know/am not sure
20. Have you previously participated as an investigator of a clinical trial assessing ENJAYMO™ (sutimlimab) treatment?
- Yes
 - No
 - Prefer not to answer
21. Are you involved in the CADENCE patient registry for Cold Agglutinin Disease and Cold Agglutinin Syndrome?
- Yes
 - No
 - Prefer not to answer

CLOSING

Thank you for taking the time to complete this survey.

You may now close this browser.

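### Question 13 asks whether vaccination was confirmed as up-to-date but is routed as if it asked whether status was checked, so prescribers who acted on a gap may miss Questions 16 to 18

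*Protocol*

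**What the plan says.** All items here concern the patient most recently prescribed the product and are put to prescribers only (Protocol, Annex 3).

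- **Question 13:** "did you confirm that their vaccination status is up-to-date according to local guidelines or recommendations for patients with persistent complement deficiencies". The No branch reads "No → PROCEED TO QUESTION 19", and don't know goes to the same place. Only Yes leads to Question 14.
- **Question 14:** "which vaccines did you check the status of? Please select all that apply".
- **Question 15:** "was the patient up-to-date on their vaccinations". Yes and don't know go to Question 19; only No leads to Question 16.
- **Question 16:** "did you administer or prescribe vaccines to the patient". Yes leads to Question 18 and No to Question 17, which asks why vaccination was not provided.
- **Question 18:** "when were vaccinations administered relative to starting of ENJAYMO™ (sutimlimab"). It is reached through Yes at Question 16, or through the answer at Question 17 that vaccination was received elsewhere.

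Table 9-2 (section 9.2.3) has one row for "HCP confirmed vaccination status in the patient most recently prescribed ENJAYMO™" and a different row for "Vaccines up-to-date in the patient most recently prescribed ENJAYMO™".

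Implementation of vaccination is a secondary endpoint (section 9.2.2). Section 9.9.1.2 describes it as the date of vaccination against treatment start where the prescriber gave the vaccines. Section 9.7 expects possibly 10 prescribers among 50 respondents.

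**The concern.** A gate question should separate those who did something from those who did not. Question 13 asks about the act of checking and the result of the check in one sentence. Read literally, Yes means the patient was up-to-date, and the later No at Question 15 contradicts it. Yet Yes at 13 followed by No at 15 is the only route to the items on vaccines given, reason not given, and timing.

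The prescribers at risk of being lost are those who checked, found a gap and acted on it, which is the behaviour the implementation endpoint is meant to describe. Analysis cannot repair this later: a recorded No cannot be split into those who checked and those who did not, and an unasked question yields no data. Section 9.8 also bars respondents from revising an answer once they advance, and bars re-contact to clarify answers to knowledge questions.

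**Working it through.** The plan gives no figure for this point, so the check is a routing trace followed by an illustration.

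**Routing for a prescriber who checked, found a gap and vaccinated**

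| Reading of Question 13 | Answers | Path | Questions 16 and 18 answered? |
|---|---|---|---|
| (a) Literal: status was not up-to-date | 13 No | 13, 19 | No |
| (b) Confirm means check | 13 Yes, 15 No, 16 Yes | 13, 14, 15, 16, 18, 19 | Yes |
| (c) Up-to-date once vaccinated | 13 Yes, 15 Yes | 13, 14, 15, 19 | No |

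Only (b) collects the data. Question 17 matters for a prescriber who found a gap and did not vaccinate; reading (a) closes that item off too.

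**Which meaning the protocol intends.** Question 14 presupposes that a check took place. Question 15 would be redundant if Yes at 13 already meant up-to-date. Table 9-2 keeps the two variables apart. All three point to reading (b).

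**Illustration.** The input from the protocol is N = 10 prescribers (section 9.7). Assumed, not in the documents: all 10 checked, a share g found a gap and vaccinated, and a share m of those follow reading (a) while the rest follow (b).

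- Recorded as having confirmed status: N × (1 − g × m)
- Answering Questions 16 and 18: N × g × (1 − m)
- Recorded up-to-date at Question 15: N × (1 − g) out of N × (1 − g × m)

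With g = 0.4, so four prescribers acted on a gap:

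| Taking the literal reading | Confirmed status | Up-to-date at Question 15 | Answering 16 and 18 |
|---|---|---|---|
| 0 of 4 | 10/10 | 6/10 | 4 |
| 2 of 4 | 8/10 | 6/8 | 2 |
| 4 of 4 | 6/10 | 6/6 | 0 |

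If all four instead follow reading (c), Question 13 shows 10/10, Question 15 shows 10/10, and Questions 16 and 18 again have 0 respondents. The checking rate is then right, but the gaps disappear from the data.

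Varying g over 0.3, 0.5 and 0.7:

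- No literal readings (m = 0): 3, 5 and 7 respondents at Questions 16 and 18.
- Half literal (m = 0.5): 1.5, 2.5 and 3.5 expected respondents, with recorded checking of 85%, 75% and 65%.
- All literal (m = 1): 0 respondents in each case, with recorded checking of 70%, 50% and 30%.

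**The case against.** The strongest reply is that this is an ambiguity and not a wrong question. To confirm that a status is up-to-date is often understood as verifying it, and a prescriber who reads it so follows the intended path. Annex 3 also has Questions 12 to 18 displayed on one page, so the respondent may see Questions 14 and 15 beside Question 13 and infer what is meant. This stands as a limit on the size of the problem. It does not remove it: the written routing is unchanged, and mixed readings in a group of about 10 are enough to blur the result.

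A reader might infer that every prescriber who found a gap will answer No. The documents do not support that; readings (b) and (c) are also truthful. A reader might also infer that Table 9-2 defines the variable as checking. It does not: the row uses the same verb as Question 13 and lists only response categories. That checking is meant is an inference, though a well-grounded one.

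It is also fair that the endpoint is descriptive and has no success threshold, that the checking rate is tabulated under other endpoints, and that section 9.11 already warns of few responses to prescriber-only items. That warning concerns precision. It does not cover a loss that depends on whether the prescriber met a gap and acted on it.

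**Conclusion.** The point holds as a wording and routing fault with an uncertain effect. Question 13 conflicts with the branch it opens and fits poorly with the separate rows of Table 9-2. A prescriber who checked and acted may be recorded like one who never checked, or may be recorded as having had an up-to-date patient. Either way, the items on vaccines given and timing are skipped.

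The loss ranges from none to every prescriber who acted on a gap. The documents fix only the expected 10 prescribers; the share with gaps and the mix of readings are assumptions. The primary composite uses Questions 3 to 8 and is untouched, so the consequence is confined to prescriber-only descriptive results. The change is worth making because it is small and the missing answers cannot be recovered afterwards.

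**What to change.** Two items need rewording:

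1. **Question 13:** ask whether the HCP checked the patient's vaccination status, keeping the present reference to local guidance for persistent complement deficiencies. Leave the result of the check to Question 15.
2. **Question 15:** add a time point, for example by opening with *at the time you checked*. Without it, reading (c) survives the change to Question 13: a prescriber who vaccinated can still answer Yes and skip Questions 16 to 18.

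No items are added and the routing stays as it is. The cost is re-translation with independent proof-reading and signed affiliate validation in each country (section 9.1.2), plus any ethics submission required (section 10.1).

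Timing matters. The protocol is dated 05 June 2024 and section 6 plans data collection from Q2 2024, so fielding may already have begun. A second wave would use the same survey (section 9.1.1) and be pooled with the first (section 9.9.1.1). If respondents have already answered the present wording, keep it, avoid mixing versions, and report the ambiguity as a limitation of this endpoint.

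### Questions 15, 16 and 18 take one answer for all vaccines, so vaccination status can be tied to a vaccine class only in part, and provision and timing not at all when several vaccines were given

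*Protocol*

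**What the plan says.** All the items concern the patient to whom the prescriber most recently gave the product (Protocol, Annex 3).

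- Question 13 asks "did you confirm that their vaccination status is up-to-date according to local guidelines or recommendations for patients with persistent complement deficiencies". Only a Yes leads on to Question 14; the other answers go to Question 19.
- Question 14 asks "which vaccines did you check the status of? Please select all that apply". Meningococcal conjugate, meningococcal serogroup B, pneumococcal and other vaccines are separate options.
- Question 15 asks "was the patient up-to-date on their vaccinations", answered Yes, No or don't know. Yes and don't know leave for Question 19; only No continues to Question 16.
- Question 16 asks "did you administer or prescribe vaccines to the patient", again with one answer.
- Question 18 asks "when were vaccinations administered relative to starting of" treatment. It offers a single list of timings and no multiple-selection instruction.

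Table 9-2 (section 9.2.3) has the same structure. The row "Vaccines HCP checked in the patient most recently prescribed ENJAYMO™" keeps the classes apart. The row "Vaccines up-to-date in the patient most recently prescribed" is one Yes/No/don't-know variable, and provision and timing are one variable each.

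These items serve the secondary objective in section 8.2 and the secondary endpoint in section 9.2.2 on implementation of vaccination, asked of prescribers only. Sections 9.9.1.2 and 9.11 describe implementation as the date of vaccination set against the start of treatment, where the prescriber gave the vaccines. Section 9.7 expects possibly 10 prescribers among 50 respondents.

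**The concern.** The form treats the vaccine classes as distinct when it asks what was checked, and merges them when it asks what was found, what was given and when. Question 15 also drops the reference standard that Question 13 supplies and follows directly after the list of vaccines checked. A respondent can read it as covering the vaccines just ticked or as covering everything the local guideline recommends, and the two readings give different answers for the same patient.

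At stake is what the implementation endpoint can show. Section 7 says the Guide is meant to increase vaccination, and meningococcal infection is the one infection named in the Guide's risk messages. A percentage up to date that does not say for which vaccines, and a timing distribution that does not say of which vaccine, leave open whether meningococcal vaccination was in place.

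**Working it through.** **Precision figure in the plan.** Section 9.7 uses the simple asymptotic half-width 1.96 × √(p(1−p)/n). For n = 50 and p = 0.80 this is 1.96 × √(0.16/50) = 0.111, or 11.1 points, as stated. The point made here does not depend on that figure. The same formula for the expected 10 prescribers gives 1.96 × √(0.16/10) = 0.248, or about 25 points.

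**What Questions 14 and 15 identify together.** The three named classes allow 2³ − 1 = 7 non-empty selections at Question 14. Suppose first that the respondent reads Question 15 as covering the vaccines checked.

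| Question 15 | Ticked at Question 14 | Selections | Known about meningococcal status |
|---|---|---|---|
| Yes | both meningococcal types, with or without pneumococcal | 2 of 7 | both up to date |
| Yes | one meningococcal type, with or without pneumococcal | 4 of 7 | that type up to date, the other unknown |
| Yes | pneumococcal only | 1 of 7 | nothing, yet the variable reads up to date |
| No | one meningococcal type alone | 2 of 7 | that type not up to date |
| No | two or more classes | 4 of 7 | the lapsed class is not identified |
| No | pneumococcal only | 1 of 7 | nothing |
| Don't know | any | 7 of 7 | nothing |

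These are counts of possible answer patterns, not probabilities.

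Suppose instead that the respondent reads Question 15 as covering all recommended vaccines, taken here to be the three classes. A Yes then means all are current, and a No never shows which lapsed. The form does not record which reading was used.

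**Questions 16 to 18.** Question 16 names no vaccine, so a Yes does not say which vaccine was given or prescribed. Question 18 is reached only after No at Question 15, followed either by Yes at Question 16 or by vaccination elsewhere at Question 17. If two vaccines were given at different intervals before treatment, one answer cannot describe both. A respondent who answers Yes at Question 15 on the strength of one class goes to Question 19 and supplies no provision or timing data.

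**Size.** One respondent is worth 100/k points when k prescribers answer Question 15. At k = 10 this is 10 points. Because Question 15 needs a Yes at Question 13, k may be smaller; at an assumed k = 5 it is 20 points. The documents give no figure for how often only some classes are checked. Purely as an illustration, take k = 10 and 8 Yes answers. If between 0 and 3 of those rested on pneumococcal only, the reported 8/10 (80%) would contain between 8/10 (80%) and (8 − 3)/10 (50%) with at least one meningococcal type checked.

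**The case against.** The strongest reply starts from Question 13. Only prescribers who say they confirmed status against the local guideline reach Question 15, Question 5 has already named the three classes, and Questions 12 to 18 appear on one page. On that reading Question 15 plainly means the guideline set, and a patient current for one vaccine and lapsed for another is correctly answered No. This has force: it is wrong to say that such a patient has no correct answer. It does not make the scope certain, because Question 15 omits the standard and comes straight after an item about which vaccines were checked.

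A second reply is that Questions 14 and 15 come from the same respondent and can be cross-tabulated, and that such rules belong in the statistical analysis plan. That is right for status, and the absence of a linking rule from the Protocol is not a defect. It does not help with provision and timing. No derivation can create vaccine-level answers that were never collected, and provision and timing are how sections 9.9.1.2 and 9.11 describe implementation.

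Third, the endpoint is secondary and descriptive, the study has no a priori hypothesis, and section 9.11 already concedes low precision for these items. All of this stands and limits the weight of the point.

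A reader might go further and infer that a prescriber who checked one vaccine is scored as having a fully up-to-date patient, or that meningococcal status is lost altogether. Neither is supported. No scoring rule in the Protocol forces that classification, the respondent may answer No or don't know, and some answer patterns do identify meningococcal status.

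**Conclusion.** The point holds as a limitation of the questionnaire. A Yes at Question 15 can rest on one checked class. A No with two or more classes ticked does not identify the lapsed class. Provision and timing cannot be assigned to a vaccine when several were given or were given at different times. Meningococcal status is recoverable in part through Question 14.

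The effect is confined to the prescriber-only vaccination items, at 10 points per misclassified respondent if 10 prescribers answer. The primary composite uses Questions 3 to 8 and is untouched. That the up-to-date percentage will be overstated does not follow: it can be, but by how much depends on the frequency of partial checking, which the documents do not give.

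**What to change.** **Before launch.** Ask Questions 15, 16 and 18 once per vaccine class listed in Question 14, for example as a grid with one row per class. Repeat the local-guideline wording of Question 13 in Question 15, and change the status, provision and timing rows of Table 9-2 to match.

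**If the form is already in use.** Section 6 places the start of data collection in Q2 2024, subject to launch dates, so this may be the case. Keep the form unchanged for both waves: section 9.1.1 plans the second wave as the same survey, and section 9.9.1.1 pools the two, so a grid introduced only in the second wave would create two formats to reconcile. Report Question 15 by Question 14 pattern, and do not present a Yes on its own as full coverage. State that provision and timing are not vaccine-specific.

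Any derived variable for confirmed up-to-date status should require the classes that each country's guideline calls for. Requiring all three everywhere would replace the local standard in section 8.1 and Question 13 with a uniform one that the documents do not support.

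**Cost.** Before launch, a few more clicks for about 10 respondents and a revision of three table rows. Afterwards, one cross-tabulation. The reported percentage may be less favourable.

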Annex 4 ENCePP checklist for study protocols

Doc.Ref. EMA/540136/2009

ENCePP Checklist for Study Protocols (Revision 4)

Adopted by the ENCePP Steering Group on 15/10/2018

The European Network of Centres for Pharmacoepidemiology and Pharmacovigilance (ENCePP) welcomes innovative designs and new methods of research. This Checklist has been developed by ENCePP to stimulate consideration of important principles when designing and writing a pharmacoepidemiological or pharmacovigilance study protocol. The Checklist is intended to promote the quality of such studies, not their uniformity. The user is also referred to the ENCePP Guide on Methodological Standards in Pharmacoepidemiology, which reviews and gives direct electronic access to guidance for research in pharmacoepidemiology and pharmacovigilance.

For each question of the Checklist, the investigator should indicate whether or not it has been addressed in the study protocol. If the answer is "Yes", the section number of the protocol where this issue has been discussed should be specified. It is possible that some questions do not apply to a particular study (for example, in the case of an innovative study design). In this case, the answer 'N/A' (Not Applicable) can be checked and the "Comments" field included for each section should be used to explain why. The "Comments" field can also be used to elaborate on a "No" answer.

This Checklist should be included as an Annex by marketing authorisation holders when submitting the protocol of a non-interventional post-authorisation safety study (PASS) to a regulatory authority (see the Guidance on the format and content of the protocol of non-interventional post-authorisation safety studies). The Checklist is a supporting document and does not replace the format of the protocol for PASS presented in the Guidance and Module VIII of the Good pharmacovigilance practices (GVP).

Study title: A Survey of Healthcare Professionals in Europe to Evaluate the Effectiveness of the ENJAYMO™ Physician's Guide

EU PAS Register® number: To be assigned when study is registered
Study reference number (if applicable): CEF-0205

Section 1: Milestones	Yes	No	N/A	Section Number
1.1 Does the protocol specify timelines for				6
1.1.1 Start of data collection ¹				
1.1.2 End of data collection ²				
1.1.3 Progress report(s)				
1.1.4 Interim report(s)				
1.1.5 Registration in the EU PAS Register®				
1.1.6 Final report of study results.				

¹ Date from which information on the first study is first recorded in the study dataset or, in the case of secondary use of data, the date from which data extraction starts.

² Date from which the analytical dataset is completely available.

Comments:

--

Section 2: Research question	Yes	No	N/A	Section Number
2.1 Does the formulation of the research question and objectives clearly explain:				
2.1.1 Why the study is conducted? (e.g. to address an important public health concern, a risk identified in the risk management plan, an emerging safety issue)				7
2.1.2 The objective(s) of the study?				8
2.1.3 The target population? (i.e. population or subgroup to whom the study results are intended to be generalised)				9.4
2.1.4 Which hypothesis(-es) is (are) to be tested?				
2.1.5 If applicable, that there is no a priori hypothesis?				8

Comments:

--

Section 3: Study design	Yes	No	N/A	Section Number
3.1 Is the study design described? (e.g. cohort, case-control, cross-sectional, other design)				9.3
3.2 Does the protocol specify whether the study is based on primary, secondary or combined data collection?				9.1, 9.8
3.3 Does the protocol specify measures of occurrence? (e.g., rate, risk, prevalence)				
3.4 Does the protocol specify measure(s) of association? (e.g. risk, odds ratio, excess risk, rate ratio, hazard ratio, risk/rate difference, number needed to harm (NNH))				
3.5 Does the protocol describe the approach for the collection and reporting of adverse events/adverse reactions? (e.g. adverse events that will not be collected in case of primary data collection)				11

Comments:

Measures of occurrence are levels of knowledge, expressed as the percentages of respondents with correct answers to questions regarding knowledge of information included in the ENJAYMO™ Physician's Guide.
--

Section 4: Source and study populations	Yes	No	N/A	Section Number
4.1 Is the source population described?				9.1.1, 9.4
4.2 Is the planned study population defined in terms of:				
4.2.1 Study time period				9.1.1, 9.3
4.2.2 Age and sex				
4.2.3 Country of origin				9.1.1, 9.3
4.2.4 Disease/indication				
4.2.5 Duration of follow-up				
4.3 Does the protocol define how the study population will be sampled from the source population? (e.g. event or inclusion/exclusion criteria)				9.1.1, 9.4, 9.7

Comments:

This is a cross-sectional study of HCPs, who treat patients diagnosed with CAD, and who can prescribe ENJAYMO™. Age, sex, disease, and duration of follow-up are all not applicable.

Section 5: Exposure definition and measurement	Yes	No	N/A	Section Number
5.1 Does the protocol describe how the study exposure is defined and measured? (e.g. operational details for defining and categorising exposure, measurement of dose and duration of drug exposure)				
5.2 Does the protocol address the validity of the exposure measurement? (e.g. precision, accuracy, use of validation sub-study)				
5.3 Is exposure categorised according to time windows?				
5.4 Is intensity of exposure addressed? (e.g. dose, duration)				
5.5 Is exposure categorised based on biological mechanism of action and taking into account the pharmacokinetics and pharmacodynamics of the drug?				
5.6 Is (are) (an) appropriate comparator(s) identified?				

Comments:

This is a non-interventional study that aims to test knowledge related to risk minimisation for ENJAYMO™. Although the ENJAYMO™ Physician's Guide may be considered an educational intervention, exposure to it/use of it is not specifically required in order to participate in this study.

Section 6: Outcome definition and measurement	Yes	No	N/A	Section Number
6.1 Does the protocol specify the primary and secondary (if applicable) outcome(s) to be investigated?				8, 9.2
6.2 Does the protocol describe how the outcomes are defined and measured?				9.2
6.3 Does the protocol address the validity of outcome measurement? (e.g. precision, accuracy, sensitivity, specificity, positive predictive value, use of validation sub-study)				9.1, 9.2, 9.7, 9.11
6.4 Does the protocol describe specific outcomes relevant for Health Technology Assessment? (e.g. HRQoL, QALYs, DALYs, health care services utilisation, burden of disease or treatment, compliance, disease management)				

Comments:

--

Section 7: Bias	Yes	No	N/A	Section Number
7.1 Does the protocol address ways to measure confounding? (e.g. confounding by indication)				9.9.2.2
7.2 Does the protocol address selection bias? (e.g. healthy user/adherer bias)				9.11
7.3 Does the protocol address information bias? (e.g. misclassification of exposure and outcomes, time-related bias)				9.1.2

Comments:

--

Section 8: Effect measure modification	Yes	No	N/A	Section Number
8.1 Does the protocol address effect modifiers? (e.g. collection of data on known effect modifiers, sub-group analyses, anticipated direction of effect)				9.9.2.2

Comments:

--

Section 9: Data sources	Yes	No	N/A	Section Number
9.1 Does the protocol describe the data source(s) used in the study for the ascertainment of:				
9.1.1 Exposure? (e.g. pharmacy dispensing, general practice prescribing, claims data, self-report, face-to-face interview)				

Section 9: Data sources	Yes	No	N/A	Section Number
9.1.2 Outcomes? (e.g. clinical records, laboratory markers or values, claims data, self-report, patient interview including scales and questionnaires, vital statistics)				9.1.1, 9.2
9.1.3 Covariates and other characteristics?				9.6
9.2 Does the protocol describe the information available from the data source(s) on:				
9.2.1 Exposure? (e.g. date of dispensing, drug quantity, dose, number of days of supply prescription, daily dosage, prescriber)				
9.2.2 Outcomes? (e.g. date of occurrence, multiple event, severity measures related to event)				9.1.1, 9.2
9.2.3 Covariates and other characteristics? (e.g. age, sex, clinical and drug use history, co-morbidity, co-medications, lifestyle)				9.6
9.3 Is a coding system described for:				
9.3.1 Exposure? (e.g. WHO Drug Dictionary, Anatomical Therapeutic Chemical (ATC) Classification System)				
9.3.2 Outcomes? (e.g. International Classification of Diseases (ICD), Medical Dictionary for Regulatory Activities (MedDRA))				
9.3.3 Covariates and other characteristics?				
9.4 Is a linkage method between data sources described? (e.g. based on a unique identifier or other)				

Comments:

--

Section 10: Analysis plan	Yes	No	N/A	Section Number
10.1 Are the statistical methods and the reason for their choice described?				9.9
10.2 Is study size and/or statistical precision estimated?				9.7, 9.9.1
10.3 Are descriptive analyses included?				9.9
10.4 Are stratified analyses included?				9.9
10.5 Does the plan describe methods for analytic control of confounding?				9.9
10.6 Does the plan describe methods for analytic control of outcome misclassification?				
10.7 Does the plan describe methods for handling missing data?				9.9.1.2
10.8 Are relevant sensitivity analyses described?				9.9.1.2

Comments:

An independent statistical analysis plan will be developed to provide further details.

Section 11: Data management and quality control	Yes	No	N/A	Section Number
11.1 Does the protocol provide information on data storage? (e.g. software and IT environment, database maintenance and anti-fraud protection, archiving)				9.8
11.2 Are methods of quality assurance described?				9.8, 9.10
11.3 Is there a system in place for independent review of study results?				

Comments:

Results will be communicated to applicable health authorities within the agreed timeframe.

Section 12: Limitations	Yes	No	N/A	Section Number
12.1 Does the protocol discuss the impact on the study results of:				
12.1.1 Selection bias?				9.11
12.1.2 Information bias?				
12.1.3 Residual/unmeasured confounding? (e.g. anticipated direction and magnitude of such biases, validation sub-study, use of validation and external data, analytical methods).				
12.2 Does the protocol discuss study feasibility? (e.g. study size, anticipated exposure uptake, duration of follow-up in a cohort study, patient recruitment, precision of the estimates)				9.1.1, 9.3, 9.7, 9.9.1, 9.11

Comments:

Section 13: Ethical/data protection issues	Yes	No	N/A	Section Number
13.1 Have requirements of Ethics Committee/ Institutional Review Board been described?				10
13.2 Has any outcome of an ethical review procedure been addressed?				
13.3 Have data protection requirements been described?				10

Comments:

Section 14: Amendments and deviations	Yes	No	N/A	Section Number
14.1 Does the protocol include a section to document amendments and deviations?				5

Comments:

--

Section 15: Plans for communication of study results	Yes	No	N/A	Section Number
15.1 Are plans described for communicating study results (e.g. to regulatory authorities)?				12
15.2 Are plans described for disseminating study results externally, including publication?				12

[figure not shown]
Comments:

--

[figure not shown]
